## 12.3 Inclusion and Exclusion Criteria

### Inclusion Criteria:

Participants must:

- Be over the age of 18 years.
- Present with any symptoms indicative of SARS-CoV-2 infection within 0 to 5 days of symptom onset.

QuantuMDx www.quantumdx.com	Review Period	Doc. ID	Version
Document Title: Q-POC SARS-CoV-2 Assay (Q27001) Clinical Performance Study Plan	1 year	QVTP-39	1.0

- Have capacity to give informed consent.

Exclusion Criteria:

Participants must not:

- Be under the age of 18.
- Have no symptoms indicative of SARS-CoV-2 infection.
- Lack capacity to give informed consent.

Required patient and sample data to be recorded:

- Collection testing date and time
- Age
- Sex
- Country of residence
- Ethnicity
- Clinical signs and symptoms
- Time since onset of symptoms
- Clinical history
- Co-morbidities
- Medications taken or administered
- Vaccination status (SARS-CoV-2 and Influenza)
- Other relevant diagnostic data e.g., indications for testing
- Time taken between specimen collection and sample processing on Q-POC

## 12.4 Number of Specimens

Nasal mid-turbinate swab (MTSW) samples from sufficient participants to achieve a minimum target at the end of the study of:

- 50 comparator test-confirmed SARS-CoV-2 positive samples
- 500 comparator test-confirmed SARS-CoV-2 negative samples

Sample numbers chosen are in alignment with FDA recommendations in response to QuantuMDx's pre-submission Q220638.

QuantuMDx www.quantumdx.com	Review Period	Doc. ID	Version
Document Title: Q-POC SARS-CoV-2 Assay (Q27001) Clinical Performance Study Plan	1 year	QVTP-39	1.0

An adequate number of subjects (N=550) will be enrolled to achieve a minimum 50 symptomatic positive and 500 negative cases confirmed via Roche Cobas 6800 SARS-CoV-2, a FDA approved reference standard.

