## 7 Study Synopsis

Title	Q-POC SARS-CoV-2 Assay Clinical Performance Study Plan
Primary Objective	To evaluate the clinical diagnostic performance (positive percent agreement [PPA] and negative percent agreement [NPA]) of QuantuMDx's Q-POC SARS-CoV-2 Assay when running mid-turbinate nasal swab (MTSW; also known as nasal mid-turbinate, NMT) compared to Roche Cobas 6800 SARS-CoV-2 Comparator Test.
Study Design	
Prospective clinical study enrolling patients with signs and symptoms that are consistent with SARS-CoV-2. Positive and negative specimens will be run on the Q-POC SARS-CoV-2 Assay in comparison with an FDA-approved reference standard. The reference standard will be the Roche Cobas 6800 SARS-CoV-2.
 
Three clinical testing sites, located in different geographical locations of the U.S., will be used to collect SARS-CoV-2 positive and negative specimens. Testing sites may be independent from sample collection sites – i.e., there can be multiple sample specimen collection sites that feed into the three testing sites.

Study Population	
Prospectively enrolled patients >18 years of age with signs and symptoms that are indicative of SARS-CoV-2 infection.
 
Subject populations must be from the U.S. to be representative of the intended patient population(s).

 www.quantumdx.com	Review Period	Doc. ID	Version
Document Title: Q-POC SARS-CoV-2 Assay (Q27001) Clinical Performance Study Plan	1 year	QVTP-39	1.0

Intended Sample Type	Nasal mid-turbinate swab specimens (MTSW)
Sample Size	Nasal mid-turbinate swab (MTSW) swab samples from sufficient participants to achieve a minimum target at the end of the study of:  50 comparator test-confirmed SARS-CoV-2 positive samples  500 comparator test-confirmed SARS-CoV-2 negative samples.
Eligibility Criteria	Inclusion Criteria  Participants must:  Be over the age of 18 years.  Present with symptoms indicative of SARS-CoV-2 infection, within 0-5 days of symptom onset.  Have capacity to give informed consent.  Exclusion Criteria  Under the age of 18.  No symptoms of SARS-CoV-2 infection.  Lack of capacity to give informed consent.
Study Duration	The study period will start on 07NOV22 and will continue until sample collection is complete.

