## 12 Specimen Information

### 12.1 Specimen Type to be Tested

*Table 3: Claimed specimen type to be validated in this Clinical Performance Study Plan (QVTP-39)*

Anatomical Location/Sample type	Common/Uncommon Respiratory Sample Type	Diluted into Liquid?	Type of Liquid/Transport medium
Mid-turbinate nasal swab (MTSW)	Common	Yes	MSwab preservation medium

The comparator test, Roche Cobas 6800 SARS-CoV-2 Test is validated for testing nasopharyngeal swab samples (NPS); therefore, an additional set of this specimen type will be collected for the comparator test in Copan UTM.

Sample Categories:

- Category I: Fresh samples, prospectively collected and tested in an 'all comers' fashion.
- Category II: Archived samples prospectively collected, frozen, and retrospectively tested. All samples are collected and tested in an 'all comers' fashion.

[figure not shown]
 www.quantumdx.com	Review Period	Doc. ID	Version
Document Title: Q-POC SARS-CoV-2 Assay (Q27001) Clinical Performance Study Plan	1 year	QVTP-39	1.0

Ideally, Category II samples should be limited to no more than 30% of the total prospective samples enrolled in the clinical study.

[figure not shown]
Please note that Category I and II samples must be collected sequentially from all patients meeting study inclusion criteria and representing the assay's intended use population (i.e., not pre-selected) presenting at a clinical facility between two pre-determined dates. This minimizes bias and prevalence of infection in the population can be evaluated. The Category II samples should be appropriately stored (e.g., frozen at -70°C to -80°C).

It is anticipated that within this clinical study both the comparator and candidate samples will be tested under the Category I conditions.

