### 13.1 Data Validity

Upon completion of each Q-POC run, the instrument should display the test status as 'VALID'. If any other test status is displayed, the run should be discarded.

The comparator RT-PCR assay, Roche cobas® SARS-CoV-2, uses two SARS-CoV-2 nucleocapsid targets. Target 1 is specific to the SARS-CoV-2 virus, but Target 2 is a pan-Sarbecovirus region of the nucleocapsid that is conserved and detects both SARS-CoV-1 and SARS-CoV-2. This comparator RT-PCR assay considers samples which are positive for Target 1 as positive for SARS-CoV-2 virus regardless of the status of Target 2 which can be invalid, negative, or positive

QuantuMDx www.quantumdx.com	Review Period	Doc. ID	Version
Document Title: Q-POC SARS-CoV-2 Assay (Q27001) Clinical Performance Study Plan	1 year	QVTP-39	1.0

and the sample is still SARS-CoV-2 positive if Target 1 is positive. If Target 2 is positive and Target 1 is either negative or invalid, then the result is a presumptive positive due to Target 2's promiscuity among Sarbecovirus members. The decision has been made to consider all presumptive positive results as invalid for this clinical performance study. Only the result of "SARS-CoV-2 RNA detected", according to the manufacturer's instructions for use, will be counted as positive in the clinical performance evaluation data analysis.

Any problems encountered during testing must also be communicated to the relevant facilitator(s) and to QuantuMDx.

Any invalid tests should be repeated at least once.

External Quality Controls will be run as per the Q-POC SARS-CoV-2 Assay product IFU and Roche cobas® SARS-CoV-2 IFU. External positive control runs must return positive results. External negative control runs must return negative results. If the incorrect result is returned, or the Q-POC™ instrument displays one of these test statuses as 'INVALID', the controls should be re-run. If repeats also fail, contact the facilitator(s) or QuantuMDx.

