## 15 Statistical Considerations

The diagnostic performance of the Q-POC SARS-CoV-2 Assay (in terms of PPA and NPA) will be determined using the Roche Cobas 6800 SARS-CoV-2 Test, as an FDA-approved reference standard comparator assay. This will be done for the entire dataset and also for subsets classified by comparator Ct-banding ( $Ct \leq 25$ ,  $25 < Ct \leq 30$ ,  $Ct > 30$ ) for SARS-CoV-2. Diagnostic performance will be assessed as follows:

- Positive Percent Agreement (PPA) will be calculated as  $100\% \times (TP / (TP + FN))$ .
- Negative Percent Agreement (NPA) will be calculated as  $100\% \times (TN / (TN + FP))$ .
- PPA and NPA will include 95% CI.

Where:

- True Positive (TP) indicates that both the Q-POC SARS-CoV-2 Assay and comparator assay returned a positive result for the target.
- False Negative (FN) indicates that the Q-POC SARS-CoV-2 Assay returned a negative result for the target, while the comparator assay returned a positive result.
- True Negative (TN) indicates that both the Q-POC SARS-CoV-2 Assay and comparator assay returned a negative result for the target.
- False Positive (FP) indicates that the Q-POC SARS-CoV-2 Assay returned a positive result for the target, while the comparator assay returned a negative result.

The performance of the Q-POC SARS-CoV-2 Assay will be presented based on the overall study (all specimens of a claimed specimen type combined) as well as stratified by site and time since symptom onset.

QuantuMDx www.quantumdx.com	Review Period	Doc. ID	Version
Document Title: Q-POC SARS-CoV-2 Assay (Q27001) Clinical Performance Study Plan	1 year	QVTP-39	1.0

The rate of invalid/indeterminate results observed during the clinical study by site and overall will be reported. The prevalence of infection observed at each clinical site as determined by the comparator and the detection rate by the Q-POC SARS-CoV-2 Assay separately will be reported.

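### Section 12.4 gives 550 as the enrolment number, but 550 is only the sum of the two minima (50 positive + 500 negative) and will almost never deliver both

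*Combined protocol and SAP*

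**What the plan says.** Section 12.4 sets the requirement as "samples from sufficient participants to achieve a minimum target at the end of the study of" 50 comparator-positive and 500 comparator-negative results, and attributes these counts to FDA pre-submission feedback. The same section then says: "An adequate number of subjects (N=550) will be enrolled to achieve a minimum 50 symptomatic positive and 500 negative cases confirmed" by the comparator. The Synopsis (section 7) repeats the two minima without the figure 550.

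Four other places bear on how that number works:

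- **Sampling (12.1).** Samples "must be collected sequentially from all patients meeting study inclusion criteria", without pre-selection, "presenting at a clinical facility between two pre-determined dates".
- **Duration (Synopsis).** "The study period will start on 07NOV22 and will continue until sample collection is complete".
- **Comparator validity (13.1).** "The decision has been made to consider all presumptive positive results as invalid for this clinical performance study". Also, "Any invalid tests should be repeated at least once".
- **Reporting (15).** "The rate of invalid/indeterminate results observed during the clinical study by site and overall will be reported".

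The plan states no expected prevalence, no allowance for unclassified results, and no rule for what happens when the 550th subject has been enrolled.

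**The concern.** An enrolment number equal to the sum of two minima is adequate only if the split between the groups can be fixed in advance. Consecutive all-comer enrolment rules that out, since nobody knows at enrolment who will be comparator-positive. One positive fewer than 50 among 550 misses the positive minimum, and one more misses the negative minimum. A single comparator result left unclassified after repeat testing also makes 550 insufficient.

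The two directions do not matter equally. At high prevalence the negatives fall somewhat short of 500, with almost no loss of precision for negative percent agreement (NPA). At low prevalence the positives fall well short of 50, and PPA, half of the primary objective, is estimated from a much smaller group than the one aligned with FDA feedback.

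550 is the only enrolment number given, so sites and supply planners could take it as the target. The date window in 12.1 is a second possible stopping point, and it is not tied to the minima. The plan does not say which of the three governs: 550, the dates or the minima.

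**Working it through.** **Inputs from the plan.** Minimum positives 50, minimum negatives 500, stated enrolment 550 (all section 12.4); consecutive, non-selected sampling (12.1).

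**Assumptions.** Comparator-positive prevalence *p* and the rate *q* of comparator results left unclassified are not in the plan, so ranges are shown. Subjects are treated as independent with a common *p*.

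**Step 1. The plan's figure.** 50 + 500 = 550 exactly, with no margin.

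**Step 2. Stop at 550, all comparator results definite.** Let X ~ Binomial(550, *p*) be the number of positives. Both minima require X ≥ 50 and 550 − X ≥ 500, that is, X = 50. So

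P(both) = C(550, 50) · *p*^50 · (1 − *p*)^500,

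which is largest at *p* = 50/550 = 9.09%, where it equals 0.0591. A normal approximation agrees: 1/√(2π · 550 · (1/11) · (10/11)) = 1/√(2π · 45.45) = 0.059.

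**Step 3. Enrol until both minima are met.** Let T be the total enrolled at that point, and X_n the number of positives among the first *n*. Then P(T ≤ n) = P(50 ≤ X_n ≤ n − 500), and

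- P(T > 550) = 1 − P(X = 50) ≥ 1 − 0.0591 = 0.941 at any *p*;
- mean T = 550 + Σ over n ≥ 550 of [1 − P(T ≤ n)];
- enrolment for a 90% chance of both = smallest n with P(T ≤ n) ≥ 0.90.

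| Assumed prevalence | P(both minima at 550) | P(≥ 50 positives at 550) | Mean T | n for 90% chance |
|---|---|---|---|---|
| 5% | 0.002% | 0.005% | 1000 | 1180 |
| 7% | 1.1% | 3.7% | 715 | 842 |
| 8% | 3.9% | 19% | 633 | 736 |
| 9.09% | 5.9% | 52% | 582 | 647 |
| 10% | 4.6% | 78% | 566 | 588 |
| 12% | 0.5% | 99% | 569 | 580 |
| 15% | 0.001% | >99.9% | 588 | 601 |
| 20% | about 0 | >99.9% | 625 | 641 |
| 30% | about 0 | >99.9% | 714 | 737 |

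Hand check of the means where one minimum dominates: 50/0.05 = 1000; 500/0.80 = 625; 500/0.70 = 714. In a search over *p* in steps of 0.001, the smallest 90% enrolment is 574, at about 10.5% prevalence.

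**Step 4. Unclassified comparator results.** With 550 enrolled, none may be lost, so the maximum becomes (1 − *q*)^550 × 0.0591:

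- *q* = 0.5%: 0.0635 × 0.0591 = 0.38%;
- *q* = 1%: 0.00398 × 0.0591 = 0.02%.

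A Q-POC run that is not valid does not reduce these comparator-defined counts, but it does reduce the pairs available for PPA and NPA.

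**Step 5. Unequal site prevalence.** Take three sites of 183, 183 and 184 subjects with 50 expected positives in all. The chance of exactly 50 is 6.0% when site prevalences are 3%, 9% and about 15%, and 6.6% when every positive comes from one site.

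**Step 6. Precision if enrolment stops at 550 (95% Wilson intervals, illustrative counts).**

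- 5% prevalence: 550 × 0.05 = 27.5, about 27 positives. PPA 26/27: 81.7% to 99.3%, against 86.5% to 98.9% for 48/50.
- 15% prevalence: 550 × 0.85 = 467.5, about 468 negatives. NPA 459/468: 96.4% to 99.0%, against 96.4% to 98.9% for 490/500.

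**The case against.** The strongest reply is that the plan never says enrolment stops at 550. Section 12.4 and the Synopsis commit to as many participants as the minima need, and the Synopsis leaves the end date open. On that reading the minima govern, 550 is just their sum, and an overrun affects budget and timing without biasing PPA or NPA. This is a fair reading, and under it the targets are attainable. It does not rescue the sentence, because the same reading makes 550 too small as the number enrolled at least 94% of the time. The 5.9% and 94.1% are one calculation seen from two sides, not two separate defects.

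A second reply is that the joint criterion is harsh, since it counts 51 positives and 499 negatives as a failure. At 9.09% prevalence, 550 subjects give 45 to 60 positives with 73% probability, and the precision lost within that range is small. That is right about practical harm, and the chance of at least 50 positives is the more informative column in the table. The strictness nevertheless comes from the plan, which calls both counts minima.

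Third, the harmful case needs low prevalence together with a stop at 550 or at a closing date. The plan gives no prevalence, and the visible text sets no acceptance limit for PPA or NPA that a wider interval would fail. This stands, and it is why the point is not fatal. Similarly, repeat testing reduces comparator losses, so the 0.5% and 1% rates are illustrations only.

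**Conclusion.** The concern holds. As an enrolment number for minima of 50 and 500, 550 is wrong on either reading. If enrolment stops there, both minima are met with at most 5.9% probability, and less once any comparator results stay unclassified. If enrolment runs until both are met, the total exceeds 550 with at least 94.1% probability. Both bounds hold at every prevalence but assume independent subjects with a common prevalence; the site mixtures examined move the 5.9% no higher than 6.6%. The mean totals, 90% enrolments and interval widths depend on assumed prevalences.

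This should be fixed but is not fatal. The 50/500 targets are not in dispute and remain attainable if enrolment continues. What matters most is avoiding a stop at 550 when prevalence is below about 9%: at 8% the chance of reaching 50 positives is 19%, and at 5% it is close to nil.

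**What to change.** In section 12.4, restate 550 as the minimum number of subjects with a definite comparator result, preferably of evaluable Q-POC/comparator pairs. State that consecutive all-comer enrolment continues until both 50 comparator-positive and 500 comparator-negative results are reached, so total enrolment is expected to exceed 550.

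As secondary edits, align the date-window phrase in 12.1 and the duration line in the Synopsis with that rule, and say which governs if the window closes before both minima are met. If 550 is to stay as a fixed size, present 50 and 500 as expected counts at about 9.1% prevalence, not as minima. A short table of projected enrolment by assumed prevalence would help planning but is optional.

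The cost is one sentence in 12.4, one phrase in 12.1 and one line in the Synopsis. The targets, the tests and the analysis are unchanged. Enrolment beyond 550 is already implied by the plan's commitment to reach both minima.

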## 12.5 Specimen Storage, Handling, Transport, and Disposal

Once recruited, a healthcare professional will take a sample per subject for the comparator test, following the manufacturer's Instructions For Use (IFU) in one nostril. MTSW samples will be taken from the opposite nostril (that was not swabbed for the comparator NPS sample), using Copan FLOQ Swabs and placed into MSwab buffer (Q14-116-P02), for the test under investigation. In instances where opposite nostrils cannot be swabbed for both the comparator and the test under investigation, a 15 minute wait period to allow for viral reloading must occur between collecting both the comparator and the test samples on the same nostril.

Comparator RT-PCR samples will be shipped overnight with ice packs as they are collected and processed for testing within 48 hours of collection. Comparator RT-PCR samples will be stored frozen at -70°C to -80°C after testing; they will be defrosted and brought up to room temperature immediately before re-testing, if required. Test MTSW samples will be tested as soon as possible following collection, however if time is required between specimen collection and testing, the samples must be stored at 2-8 °C for up to 24 hours. Test samples must also be stored at 2-8 °C whilst the Q-POC test is running.

Following testing (and any subsequent re-testing), residual samples will be stored between -70°C to -80°C for retesting of any discordant results. Once the study is completed, the samples will be disposed of within biohazardous waste.

## 13 Clinical Performance Study Procedures

NPS samples will be tested on the Roche Cobas 6800 SARS-CoV-2 Test. A 400 µL aliquot of MTSW sample will be inserted into the Q-POC SARS-CoV-2 Assay test cassette and run on the Q-POC instrument.

Test and comparator assays will be run on their respective sample types.

### 13.1 Data Validity

Upon completion of each Q-POC run, the instrument should display the test status as 'VALID'. If any other test status is displayed, the run should be discarded.

The comparator RT-PCR assay, Roche cobas® SARS-CoV-2, uses two SARS-CoV-2 nucleocapsid targets. Target 1 is specific to the SARS-CoV-2 virus, but Target 2 is a pan-Sarbecovirus region of the nucleocapsid that is conserved and detects both SARS-CoV-1 and SARS-CoV-2. This comparator RT-PCR assay considers samples which are positive for Target 1 as positive for SARS-CoV-2 virus regardless of the status of Target 2 which can be invalid, negative, or positive

QuantuMDx www.quantumdx.com	Review Period	Doc. ID	Version
Document Title: Q-POC SARS-CoV-2 Assay (Q27001) Clinical Performance Study Plan	1 year	QVTP-39	1.0

and the sample is still SARS-CoV-2 positive if Target 1 is positive. If Target 2 is positive and Target 1 is either negative or invalid, then the result is a presumptive positive due to Target 2's promiscuity among Sarbecovirus members. The decision has been made to consider all presumptive positive results as invalid for this clinical performance study. Only the result of "SARS-CoV-2 RNA detected", according to the manufacturer's instructions for use, will be counted as positive in the clinical performance evaluation data analysis.

Any problems encountered during testing must also be communicated to the relevant facilitator(s) and to QuantuMDx.

Any invalid tests should be repeated at least once.

External Quality Controls will be run as per the Q-POC SARS-CoV-2 Assay product IFU and Roche cobas® SARS-CoV-2 IFU. External positive control runs must return positive results. External negative control runs must return negative results. If the incorrect result is returned, or the Q-POC™ instrument displays one of these test statuses as 'INVALID', the controls should be re-run. If repeats also fail, contact the facilitator(s) or QuantuMDx.

### 13.2 Discordance Analysis

Any discrepant results will be investigated via repeat testing using an alternative FDA approved RT-PCR test. Discrepant analysis will not be used to adjust PPA and NPA calculations. These results can only be used to provide further information in the product IFU or academic publications. Statistical analysis of test assay performance will be conducted to determine PPA and NPA. This will be based solely on comparison of Q-POC SARS-CoV-2 Assay and Roche Cobas 6800 SARS-CoV-2 Test results.

## 14 Monitoring Plan and Data Management

Study monitoring shall ensure

- investigators adhere to the CPSP,
- study data are accurate and complete, and
- ethical conduct of the study, e.g. the rights and well-being of study subjects are protected.

One or more qualified monitors shall be appointed. Monitors shall be:

- qualified through training and experience as well as scientific or clinical knowledge,
- knowledgeable on the specific activities to be monitored, the CPSP, and any other relevant requirements, and
- trained on the relevant quality assurance procedures as well as any special procedures for monitoring a specific clinical performance study. Training shall be documented in the study master files.

QuantuMDx www.quantumdx.com	Review Period	Doc. ID	Version
Document Title: Q-POC SARS-CoV-2 Assay (Q27001) Clinical Performance Study Plan	1 year	QVTP-39	1.0

Study data will be captured in the case report forms (CRFs) by the study staff. Paper forms will be filled in during the study and transcribed into electronic forms (smartsheet) which will feed into a spreadsheet. The paper forms will also be scanned and uploaded to the spreadsheet. Access to the data collection system will be provided to members of the study site who have been delegated data collection and entry responsibilities by the site PI and who have completed training on the EDC system.

The data recorded in the CRFs will be source-verified from study-related source documents. Quality Control checks will take place to verify that the smartsheet MDF matches the scans of the paper source CRFs. The investigator shall ensure that all data on the CRFs are complete, accurate, and consistent with source documentation. A monitor from the Sponsor (or designee) will review the CRFs for completeness and accuracy.

The investigator will anonymise patient data so that no identifiable information is kept. Data arising from the administration of the index and reference tests, e.g. graphs and other outputs will be collected. All data related to the evaluation will be stored; raw and unanalysed data files will be shared with QuantuMDx.

